Appendix 2. Schedule of Activities

Schedule of Activities, Protocol I1F-MC-RHBQ

CRF Visit (V) Number	Screening		Baseline Randomization	Blinded Treatment Period (Period 2)				
	V1		V2	V3	V4	V5	V6	V7
Weeks since Randomization			W0	W1	W2	W4	W8	W12
Study Days	-30 to -7 d	V1A: 2-3 d post-V1	1	7 ± 2d	14 ± 2d	28 ± 2d	56 ± 2d	84 ± 4d
Informed consent	X							
Complete medical history	X							
Demographics ^a	X							
Sociodemographics ^b			X					X
Physical examination ^c	X		X					X
Perianal/gluteal cleft characteristics examination	X		X					X
Inclusion/exclusion criteria ^d	X		X					
Body temperature			X					
Height			X					
Weight			X					X
Waist circumference			X					
Vital signs (BP and pulse)	X		X ^e	X	X	X	X	X ^e
Consumption habits ^f			X					
Concomitant medications	X		X	X	X	X	X	X
Review preexisting conditions/AEs			X	X	X	X	X	X
Randomization			X					
Administer IP on site			X					X

	Screening		Baseline Randomization	Blinded Treatment Dosing Period (Period 2)				
CRF Visit (V) Number	V1		V2	V3	V4	V5	V6	V7
Weeks since Randomization			W0	W1	W2	W4	W8	W12
Study Days	-30 to -7 d	V1A: 2-3 d post-V1	1	7 ± 2d	14 ± 2d	28 ± 2d	56 ± 2d	84 ± 4d
Dispense IP			X		X	X	X	X
Provide SDALg			X		X	X	X	X
Collect, review, and enter data from SDAL			X		X	X	X	X
Review e-diary				X	X	X	X	X
Dispense e-diary (includes GPSS, GPSIS, and SFQ)	X							
Collect e-diary								X
Clinical Efficacy/Health Outcomes								
sPGA (overall)	X		X	X	X	X	X	X
sPGA of Genitalia ^h	X		X	X	X	X	X	X
PASI (overall)	X		X	X	X	X	X	X
mGPASI ⁱ	X		X	X	X	X	X	X
BSA	X		X ^j	X	X	X ^j	X	X ^j
Fitzpatrick skin type			X					
GPSS ^k	Daily from Screening (V1) to Week 12 (V7)							X
GPSIS ^k	Weekly from Screening (V1) to Week 12 (V7)							X
SFQ ^k	Weekly from Screening (V1) to Week 12 (V7)							X
PatGA-Genital			X	X	X	X	X	X
Touch avoidance NRS			X		X	X	X	X

CRF Visit (V) Number	Screening		Baseline Randomization	Blinded Treatment Dosing Period (Period 2)				
	V1		V2	V3	V4	V5	V6	V7
Weeks since Randomization			W0	W1	W2	W4	W8	W12
Study Days	-30 to -7 d	V1A: 2-3 d post-V1	1	7 ± 2d	14 ± 2d	28 ± 2d	56 ± 2d	84 ± 4d
SF-36			X					X
DLQI			X		X	X	X	X
QIDS-SR16	X		X					X
C-SSRS [§]			X	X	X	X	X	X
Self-Harm Supplement Form [§]			X	X	X	X	X	X
CAPP (genital subindex)			X					X
Laboratory Tests								
Administer PPD/QuantiFERON [®] -TB Gold/T-SPOT [®] 1	X							
Read PPD		X						
Chest x-ray ^m	X							
ECG	X							
HIV/HCV	X							
HBV ⁿ	X		X					X
FSH ^o	X							
Serum pregnancy test ^p	X							

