6.10. Efficacy Analyses

[Table RHBQ.6.3](#) includes the description and derivation of the efficacy variables.

[Table RHBQ.6.4](#) includes the description and derivation of the patient reported assessments and health outcome variables. An e-diary will be used to collect GPSS daily, GPSIS, and SFQ weekly, up to Week 12 (Visit 7); thereafter, patients will answer these questions only at scheduled study visits. At Week 12 (Visit 7), patients will complete these scales on site before completion of any other assessments.

[Table RHBQ.6.5](#) provides the detailed analyses including analysis type, method and imputation, population, time point, and treatment group comparisons for primary, secondary and selected exploratory efficacy and health outcome analyses.

Table RHBQ.6.3. Description and Derivation of Efficacy Variables

Measure	Description	Variable	Derivation	Imputation Approach if Components are Missing
sPGA of Genitalia	The Static Physician Global Assessment (sPGA) of Genitalia score is based on a combination of erythema and the secondary features (plaque elevation and/or scale). For the analysis of responses, the patient’s psoriasis is assessed as follows: 0 = clear 1 = minimal 2 = mild 3 = moderate 4 = severe 5 = very severe	sPGA of Genitalia score	Ranges from 0 to 5: clear (0), minimal (1), mild (2), moderate (3), severe (4), or very severe (5).	Single item. Missing if the sPGA of Genitalia score is missing
		sPGA of Genitalia (0,1)	A sPGA of Genitalia assessed as either 0 or 1.	Missing if sPGA score of Genitalia score is missing
		sPGA of Genitalia (0)	A sPGA of Genitalia assessed as 0.	Missing if sPGA score of Genitalia score is missing

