GPSS	
The Genital Psoriasis Symptoms Scale (GPSS) is a patient-administered assessment of 8 symptoms: itch, pain, discomfort, stinging, burning, redness, scaling, and cracking. Respondents are asked to answer the questions based on their psoriasis symptoms in the respective genital areas.
 
The overall severity for each individual symptom from patient's genital psoriasis is indicated by selecting the number from an NRS of 0 to 10 that best describes the worst level of each symptom in the genital area in the past 24 hours, where 0 (= no severity) and 10 (worst imaginable severity).
 
The symptom severity scores, ranging from 0 to 10, are the values of the selected numbers indicated by the patient on the instrument's horizontal scale. Each of the 8 individual items will receive a score of 0 to 10 and will be reported as item scores for itch, pain, discomfort, stinging, burning, redness, scaling, and cracking. In addition, a total score ranging from 0 (no genital psoriasis symptoms) to 80 (worst imaginable genital psoriasis symptoms) will be reported.
	GPSS total score	
The GPSS total score will be calculated by summing the individual item scores as follows: GPSS = itch NRS + pain NRS + discomfort NRS + stinging NRS + burning NRS + redness NRS + scaling NRS + cracking NRS
 
The GPSS total score at Week 12 (Visit 7) is the average of at least 4 non-missing scores of the last 7 consecutive days. The 7-day window ends on the date of Visit 7 when the data is collected on site, and on or after the date of previous visit.
 
The GPSS total score at Week 2 (Visit 4), Week 4 (Visit 5), and Week 8 (Visit 6), is the average of at least 4 non-missing scores of the last 7 consecutive days before the date of current visit, and on or after the date of previous visit.
 
The GPSS total score at Week 1 (Visit 3), the 7-day window is before the date of Visit 3, and on or after the date of the first injection.
 
Note 1: For derivations of post-baseline visit scores, when there are less than 4 non-missing scores in the 7-day window, the window will be extended one day at a time, up to 10 days, until 4 non-missing scores are found, but the window will not be extended beyond the date of previous visit. If at least 4 non-missing scores are still not found, the visit score will be designated as missing.
 
Note 2: When 7-day duration is not present between visits, the visit score will be the average of at least 4
	If any item score is missing, the GPSS total score will be missing.

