GPSIS	
The GPSIS is a patient reported outcome measure to evaluate the impact of genital psoriasis symptoms on sexual activity. The GPSIS consists of 3 items that include 2 subscales:
 
 Sexual Activity Avoidance Subscale: This subscale includes items 1 and 2. Item 1 asks whether the patient has been sexually active in the past week. Item 2 asks how often the patient avoided sexual activity in the past week due to Genital Ps. Impact of Sexual Activity on Genital Psoriasis Symptoms Subscale: This subscale includes item 1 and 3. Item 1 asks whether the patient has been 	GPSIS Sexual Activity Avoidance Subscale score	
For Item 1, if a patient selects “no due to reasons other than my genital psoriasis”, they do not answer any additional questions on the scale and receive a score of 1 on the Sexual Activity Avoidance Subscale. If a patient responds “no due to my genital psoriasis” on GPSIS Item 1, the subscale score is set to “5” (equivalent to always avoid sexual activity due to genital psoriasis on item 2).
 
For patients who are sexually active (i.e. with a score of 0 on Item 1), a response of never, rarely, sometimes, and often on item 2 receive a score of 1, 2, 3, and 4, respectively, on the Sexual Activity Avoidance Subscale.
 
The Sexual Activity Avoidance Subscale ranges from 1 (never) to 5 (always) avoid sexual activity.
 
The Avoidance Subscale Score at Week 12 (Visit 7) is the subscale score collected at Visit 7 on site.
 
The Sexual Activity Avoidance Subscale Score at Week 2 (Visit 4), Week 4 (Visit 5), and Week 8 (Visit 6) is defined as the last non-missing subscale score collected before the date of the visit, and on or after the date of previous visit.
 
The Avoidance Subscale score at Week 1 (Visit 3) is the last non-missing subscale score before the date of Visit 3 and on or after the date of the first injection.
 
For the visit beyond Week 12 (Visit 7), the score is as being collected at that visit on site.
 
For exploratory analyses, GPSS total score at each calendar week in Blinded Treatment Period is
	
The Sexual Activity Avoidance Subscale score is missing if: Item 1 is missing; or Item 1 is answered as “Yes” but Item 2 is missing

Measure	Description	Variable	Derivation	Imputation Approach if Components are Missing

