SFQ	
The SFQ is a patient reported outcome measure to evaluate the impact of genital psoriasis symptoms on sexual frequency. It consists of 2 items that assess the impact of genital psoriasis symptoms on the frequency of sexual activity. Respondents are asked to answer the questions based on their psoriasis symptoms in the genital area.
 
Item 1 asks how many times the patient engaged in sexual activity in the past week with response options of: 2 = none/zero 1 = once 0 = two or more
 
Item 2 assesses how often genital psoriasis symptoms limited the frequency of sexual activity with the following response options: 0 = never 1 = rarely 2 = sometimes 3 = often 4 = always
	SFQ Item 1	
Item 1 score as reported in the weekly e-diaries. The score ranges from 0 to 2.
 
Item 1 Score at Week 12 (Visit 7) is the score collected at Visit 7 on site.
 
Item 1 Score at Week 2 (Visit 4), Week 4 (Visit 5), and Week 8 (Visit 6) is defined as the last non-missing score collected before the date of the visit, and on or after the date of previous visit.
 
Item 1 Score is the lasting non-missing score before the date of Visit 3 and on or after the date of the first injection.
 
For the visit beyond Week 12 (Visit 7), the score is as being collected at that visit on site.
	Missing if the item 1 score is missing
		SFQ Item 2	
Item 2 score as reported in the weekly e-diaries. The score ranges from 0 to 4.
 
Item 2 Score, at each post-baseline visit in the Blinded Treatment Period and Open-Label Treatment Period, is derived in the same manner as Item 1 Score.
	Missing if the item 2 score is missing

Measure	Description	Variable	Derivation	Imputation Approach if Components are Missing
	The individual item scores of the SFQ are reported separately. No total score is calculated for the SFQ.		
For exploratory analyses, Item 2 Score at each calendar week is examined, and defined as the last non-missing subscale score collected in the calendar week.
 
The calendar week is defined as follows: Calendar Week 1 is from study day 1 to 7; Calendar Week 2 is from study day 8 to 14; ... Calendar Week 11 is from study day 70 to 77; Calendar Week 12 is from study day 78 to the date of Visit 7.
 
Note that study day 1 is the date of the first injection during the Blinded Treatment Period.
	
		SFQ Item 2 Score of 0 or 1	Item 2 score is assessed as 0 or 1.	Missing if the item 2 score is missing

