	Time to at least a 3-point improvement in Itch NRS score	ITT Population: Patients with a baseline score of at least 3	During the Blinded Treatment Period	Kaplan Meier Analyses	Exploratory	Primary
SFQ ^a	Proportion of patients achieving SFQ item 2 score of 0 or 1	ITT Population: Patients with a baseline score of at least 2	Week 12 and other post-baseline visits ^b	Logistic regression analysis using NRI	Major Secondary #3 (at Week 12 only)	Primary
			Week 12 and other post-baseline visits ^b	Fisher’s exact test using NRI		Secondary
			At each calendar week ^c	Logistic regression analysis using NRI	Exploratory	Primary
			At each calendar week ^c	Fisher’s exact test using NRI		Secondary
	Proportion of patients at each level of SFQ item 1	ITT Population	Week 12 and other post-baseline visits ^b	Fisher’s exact test based on observed data	Exploratory	Primary
GPSIS ^a	Proportion of patients achieving Sexual Activity Avoidance	ITT Population: Patients with a baseline score of at least 3	Week 12 and other post-baseline visits ^b	Logistic regression analysis using NRI	Other secondary	Primary

Measure	Variable	Population (Section 6.1.1)	Time Point	Analysis and Imputation Method (Sections 6.1.3 and 6.3)	Objective/ Endpoint Type	Analysis Type
	Subscale score of 1 or 2		Week 12 and other post-baseline visits ^b	Fisher’s exact test using NRI		Secondary
			At each calendar week ^c	Logistic regression analysis using NRI	Exploratory	Primary
			At each calendar week ^c	Fisher’s exact test using NRI		Secondary
	Proportion of patients achieving Impact of Sexual Activity on Genital Psoriasis Symptoms Subscale score of 1 or 2	ITT Population: Patients with an Item 1 score of “0” and an Item 3 score of at least 3 at baseline	Week 12 and other post-baseline visits ^b	Logistic regression analysis using NRI	Exploratory	Primary
			Week 12 and other post-baseline visits ^b	Fisher’s exact test using NRI		Secondary

Measure	Variable	Population (Section 6.1.1)	Time Point	Analysis and Imputation Method (Sections 6.1.3 and 6.3)	Objective/ Endpoint Type	Analysis Type
			At each calendar week ^c	Logistic regression analysis using NRI	Exploratory	Primary
			At each calendar week ^c	Fisher's exact test using NRI		Secondary
mGPASI	Change from baseline in mGPASI	ITT Population	Week 12 and other post-baseline visits	MMRM	Other secondary	Primary
			Week 12 and other post-baseline visits	ANCOVA using mBOCF		Secondary

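### A fully compliant patient can have no Week 1 or Week 2 visit score for SFQ Item 2 or the GPSIS subscales, and NRI then counts that patient as a non-responder

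*SAP*

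**What the plan says.** Protocol Appendix 2 and SAP Section 6.10 have SFQ and GPSIS entered weekly in the e-diary from Visit 1. The first on-site collection after baseline is at Visit 7. Neither document fixes the diary day, ties it to the first injection, or says how long an entry stays open.

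SAP Table RHBQ.6.4 turns these entries into visit scores:

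- **Week 1, SFQ:** "Item 1 Score is the lasting non-missing score before the date of Visit 3 and on or after the date of the first injection".
- **Week 1, GPSIS avoidance:** the score "is the last non-missing subscale score before the date of Visit 3 and on or after the date of the first injection".
- **Weeks 2, 4 and 8, SFQ:** the score "is defined as the last non-missing score collected before the date of the visit, and on or after the date of previous visit". GPSIS has the matching rule, and SFQ Item 2 and the GPSIS impact subscale are derived like their companion scores.
- **Week 12:** the score recorded on site at Visit 7.

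The daily GPSS has protection that the weekly scales lack. If too few scores are found, "the window will be extended one day at a time, up to 10 days, until 4 non-missing scores are found", and a further note covers visits less than 7 days apart.

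SAP Table RHBQ.6.5 analyses the SFQ variable "Proportion of patients achieving SFQ item 2 score of 0 or 1" at Week 12 and at the other post-baseline visits, by logistic regression and Fisher's exact test with NRI. The two GPSIS responder variables are handled the same way. Each analysis is limited to patients meeting a baseline-score condition, for example SFQ Item 2 of at least 2. The same table lists calendar-week versions of these analyses as exploratory.

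**The concern.** A weekly diary is certain to yield an entry only in a window of at least 7 days, and the Week 1 and Week 2 windows can be shorter. A patient can attend every visit, take every dose and complete every diary, yet have nothing in the window. NRI then records a failure caused by the calendar and not by the patient's condition.

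The SAP's reasoning for NRI does not cover this case. Sections 6.3.1 and 6.11 treat discontinuation as failure because a patient who cannot stay on the drug will not keep its benefit, and they say every patient will therefore have an outcome. Here the patient is on treatment and adherent.

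At stake is the early time course. Week 1 and Week 2 response rates would be understated, the early treatment difference would shrink, and part of any rise from Week 2 to Week 4 would be an artefact of longer windows.

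**Working it through.** The plan gives no expected rate of missing early scores, so there is no figure of its own to reproduce.

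**Inputs.** Appendix 2 sets Visit 3 at study day 7 ± 2 (days 5 to 9) and Visit 4 at day 14 ± 2 (days 12 to 16). Table RHBQ.6.4 says: "Note that study day 1 is the date of the first injection during the Blinded Treatment Period".

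**Window length L in days.**

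- Week 1 runs from day 1 to the day before Visit 3, so L = (Visit 3 day) − 1. This is 4 to 8, and 6 on schedule.
- Week 2 runs from Visit 3 to the day before Visit 4, so L = (Visit 4 day) − (Visit 3 day). This is 12 − 9 = 3 to 16 − 5 = 11, and 7 on schedule.
- The shortest Week 4 window is 26 − 16 = 10 days and the shortest Week 8 window is 54 − 30 = 24 days. Both always hold a weekly entry.

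**Chance of no entry.** Assume one entry exactly every 7 days, with the diary day unrelated to the injection day. Then P(no entry) = max(0, 7 − L)/7.

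- Week 1 by Visit 3 day: day 5, 3/7 = 42.9%; day 6, 2/7 = 28.6%; day 7, 1/7 = 14.3%; days 8 and 9, 0%.
- Week 2 by gap between visits: 3 days, 57.1%; 4 days, 42.9%; 5 days, 28.6%; 6 days, 14.3%; 7 or more, 0%.

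**Averages over assumed visit spreads** (Visits 3 and 4 independent; triangular weights 1:2:3:2:1).

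| Visit spread | Week 1 | Week 2 |
|---|---|---|
| All on the target day | 1/7 = 14.3% | 0% |
| Triangular over ± 2 days | 10/63 = 15.9% | 52/567 = 9.2% |
| Uniform over ± 2 days | 6/35 = 17.1% | 20/175 = 11.4% |

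If Visit 3 were read as 7 days after dosing, the Week 1 column would be 0%, 6.3% and 8.6%.

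**Dependence on the diary day** (uniform visit spread).

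| Entry falls on study day | Week 1 missing | Week 2 missing |
|---|---|---|
| 1 | 0% | 16% |
| 2, 3 or 4 | 0% | 0% |
| 5 | 20% | 16% |
| 6 | 40% | 24% |
| 7 | 60% | 24% |

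Averaged over the seven days these give 1.20/7 = 17.1% and 0.80/7 = 11.4%, matching the uniform row above.

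**Effect on the comparison.** With the same missing share m in both arms, unrelated to response, NRI multiplies each response rate, and their difference, by (1 − m). Taking 40% versus 20% purely as an illustration, m = 17.1% gives 33.2% versus 16.6%, so a 20-point difference becomes 16.6 points. At m = 11.4% the rates are 35.4% and 17.7%.

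**Calendar-week scores.** Days 1–7 and 8–14 are each exactly 7 days, so a fixed 7-day cadence puts one entry in each and the structural loss is 0%.

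**The case against.** The strongest reply is that no percentage is a property of the documents. The diary day, its completion window and the visit spread are all unstated, and for some diary days the loss is nil. That is correct: the percentages are conditional. It does not remove the defect, because nothing in the plan secures a favourable diary day. A diary tied to the injection date avoids Week 1 loss but can still lose 16% at Week 2. When Visit 3 falls on days 5 to 8, it also makes the Week 1 score the day-1 entry, whose one-week recall is essentially pre-dose.

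A second reply is that little depends on these visits. Weeks 1 and 2 are not alpha-controlled, only patients meeting the baseline condition are analysed, and both blinded arms share the same visits and diary. This stands, and it limits the point to understated early rates and differences. No false-positive risk is shown.

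A third reply is that the calendar-week analyses already show the early course without these gaps. That is true, but the plan would still report visit-based Week 1 and Week 2 results that carry them.

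A reader might also infer that the Week 8 score is stale, since its window spans about 4 weeks. The rule takes the last entry, so a compliant patient's score is at most 7 days old. An older score requires missed diaries, and a 10-day limit like that for GPSS would only turn those patients into NRI failures.

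**Conclusion.** The point holds for the Week 1 and Week 2 NRI analyses of SFQ Item 2 and the GPSIS subscales. The stated rule can leave a fully compliant patient without a score and count that patient as a non-responder. Under a fixed 7-day diary with random phase, the share is about 14–17% of the analysed patients at Week 1 and 0–11% at Week 2, depending on visit spread; 0% is possible under some diary anchors. The expected effect is attenuation of both response rates and their difference, on the assumption that the loss is similar across arms.

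A reader might infer that the gated SFQ Item 2 test is weakened. The documents do not support that: Table RHBQ.6.5 makes it a major secondary endpoint at Week 12 only, and the Week 12 score is taken on site. Weeks 4 and 8 lose nothing by this route. SFQ Item 1 is analysed on observed data, so NRI does not apply to it.

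**What to change.** In SAP Tables RHBQ.6.4 and RHBQ.6.5, base the Week 1 and Week 2 NRI analyses of SFQ Item 2 and both GPSIS subscales on the calendar-week scores already defined for study days 1–7 and 8–14. Footnote that the one-week recall behind the Week 1 score is partly pre-dose. While editing, correct the GPSIS calendar-week sentence, which names the GPSS total score although it defines a GPSIS subscale score. Leave the Week 4, 8 and 12 rules unchanged, and leave SFQ Item 1 as it is, since it has no calendar-week score.

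The cost is SAP wording; the scores and their analyses are already specified. The Week 1 and Week 2 results will duplicate the exploratory calendar-week results, and after an early visit the entry used may fall up to 2 days later (7 − 5 or 14 − 12). The zero structural loss still assumes a 7-day cadence, so the SAP should also state the diary's due day and completion window.

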		2.5 point improvement in SF-36 MCS	
First calculate
 
Change from baseline $= \text{Observed SF36 MCS score} - \text{Baseline SF36 MCS score}$
 
If change from baseline is greater than or equal to 2.5, then the patient has experienced a 2.5-point improvement. If change from baseline is less than 2.5, then the patient has not experienced a 2.5-point improvement.
	Missing if the observed or baseline SF-36 MCS score is missing

Measure	Description	Variable	Derivation	Imputation Approach if Components are Missing
	
The 8 domain scores of SF-36 are:
 
 • Physical Functioning • Role-Physical • Role-Emotional • Bodily Pain • Vitality • Social Functioning • Mental Health • General Health 
The domain scores range from 0-100 with higher scores indicating better HRQoL. Domain score MCID is a ≥ 5.0-point increase from baseline.
	SF-36 Domain scores	
The details of the derivation of SF-36 domain scores are presented in Appendix 1
 
A higher domain score indicates lesser impairment.
	Missing if the SF-36 domain score is missing
		Change from baseline in SF-36 domain score	
Change from baseline $= \text{Observed SF36 domain score} - \text{Baseline SF36 domain score}$
 
A positive change indicates improvement and a negative change indicates deterioration of the condition.
	Missing if the observed or baseline SF-36 doscore is missing
		5 point improvement in SF-36 domain score	
First calculate
 
Change from baseline $= \text{Observed domain score} - \text{Baseline domain score}$
 
If change from baseline is greater than or equal to 5, then the patient has experienced a 5-point improvement. If change from baseline is less than 5, then the patient has not experienced a 5-point improvement.
	Missing if the observed or baseline SF-36 domain score is missing

Measure	Description	Variable	Derivation	Imputation Approach if Components are Missing

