PatGA-Genital	Proportion of patients with at least a 2-point improvement in PatGA-Genital	ITT Population: Patients with a baseline score of at least 2	Week 12 and other post-baseline visits	Logistic regression analysis using NRI	Other secondary	Primary
			Week 12 and other post-baseline visits	Fisher's exact test using NRI		Secondary

Measure	Variable	Population (Section 6.1.1)	Time Point	Analysis and Imputation Method (Sections 6.1.3 and 6.3)	Objective/ Endpoint Type	Analysis Type
DLQI	Change from baseline in DLQI total score	ITT Population	Week 12 and other post-baseline visits	MMRM	Other secondary	Primary
			Week 12 and other post-baseline visits	ANCOVA using mBOCF		Secondary
	Proportion of patients with no sexual impairment	ITT Population	Week 12 and other post-baseline visits	Logistic regression analysis using NRI	Other secondary	Primary
			Week 12 and other post-baseline visits	Fisher’s exact test using NRI		Secondary
	Proportion of patients with DLQI(0,1)	ITT Population	Week 12 and other post-baseline visits	Logistic regression analysis using NRI	Other secondary	Primary
			Week 12 and other post-baseline visits	Fisher’s exact test using NRI		Secondary
SF-36	Change from baseline in SF-36 PCS score	ITT Population	Week 12 and other post-baseline visits	ANCOVA using mBOCF	Other secondary	Secondary

Measure	Variable	Population (Section 6.1.1)	Time Point	Analysis and Imputation Method (Sections 6.1.3 and 6.3)	Objective/Endpoint Type	Analysis Type
	Proportion of patients with at least a 2.5 point improvement in SF-36 PCS	ITT Population	Week 12 and other post-baseline visits	Logistic regression analysis using NRI	Other secondary	Primary
			Week 12 and other post-baseline visits	Fisher’s exact test using NRI		Secondary
	Change from baseline in SF-36 MCS score	ITT Population	Week 12 and other post-baseline visits	ANCOVA using mBOCF	Other secondary	Secondary
	Proportion of patients with at least a 2.5 point improvement in SF-36 MCS	ITT Population	Week 12 and other post-baseline visits	Logistic regression analysis using NRI	Other secondary	Primary
			Week 12 and other post-baseline visits	Fisher’s exact test using NRI		Secondary
	Proportion of patients with at least a 5 point improvement in SF-36 individual domain scores	ITT Population	Week 12 and other post-baseline visits	Logistic regression analysis using NRI	Other secondary	Primary
			Week 12 and other post-baseline visits	Fisher’s exact test using NRI		Secondary

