- After this rescoring, the raw domain scores will be calculated for the scale. Domain scores are the simple algebraic sum of the final values for all items in that scale.
- All raw domain scores will be transformed to a 0-100 scale, with 0 being the lowest and 100 the highest possible score.
- Finally, the 0-100 scores will be transformed to t-score based scores. First, a z-score transformation using the mean for the respective recall period, here 1 week recall, of the 1998 general U.S. population will be used. Then the distribution of z-score is linearly transformed to have a mean of 50 and a SD of 10 by multiplying each z-score with 10 and adding 50.

The calculation of component scores is a 3-step process using the domain scores, calculated as described above:

- The standardized scores from Step 5, depending on the chosen recall period, are calculated.
- These standardized Physical and Mental component scores are calculated as the weighted sums by the factor score coefficients, derived from the 1990 general U.S. population, with the domain scores. If any domain score is missing then the aggregate Physical or Mental score will not be calculated.
- The PCS and MCS are linearly transformed by multiplying by 10 and adding 50 to obtain the aggregate t-score based scoring.

To run the scoring algorithm, the SF-36 items recorded in the study database will be exported into a comma- or tab-separated values file (*.csv, *.tab). This file will then be loaded into the Scoring Software to perform the calculations described above. The resulting raw domain scores and t-scores (domain scores) will then be exported into a comma- or tab-separated values file and imported into SAS for storage in the SDTM/ADaM datasets.

The comma- or tab-separated values file, each row will be one patient record and the first row will comprise the header columns, will have the following column specification: (to comply with the Scoring Software requirements)

eCRF Row #	Column label for export to comma- or tab-separated values file [*.csv, *.tab]	Annotated SF-36 eCRF Variable [Format: SF36V2RXX_SF36V2F1]	Item Number, Score range	eCRF question / Specification
1	GH01	[SF36V2R01_SF36V2F1]	Item # 1, Range 1-5	In general, would you say your health is:
2	HT	[SF36V2R02_SF36V2F1]	Item # 2, Range 1-5	Compared to one week ago, how would you rate your health in general now?

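### The 5-point SF-36 domain responder cut is stated on a 0-100 scale, but Appendix 1 exports raw sums and T-scores, so the cut and the analysed score do not share a metric

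*SAP*

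**What the plan says.** SAP Table RHBQ.6.4 describes the eight SF-36 domains as follows: "The domain scores range from 0-100 with higher scores indicating better HRQoL". The minimal important difference of 5.0 points follows at once, and the responder variable is defined by "If change from baseline is greater than or equal to 5, then the patient has experienced a 5-point improvement". For the scores themselves the table says "The details of the derivation of SF-36 domain scores are presented in Appendix 1".

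Appendix 1 builds the scores in three stages:

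- Raw score: "Domain scores are the simple algebraic sum of the final values for all items in that scale".
- Rescaling: "All raw domain scores will be transformed to a 0-100 scale, with 0 being the lowest and 100 the highest possible score".
- Last stage: "Finally, the 0-100 scores will be transformed to t-score based scores", with a mean of 50 and an SD of 10.

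On output it says "The resulting raw domain scores and t-scores (domain scores) will then be exported into a comma- or tab-separated values file", and the file is then read into SAS. The closing table of Appendix 1 lists one column per domain and does not name its metric.

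Table RHBQ.6.5 analyses "Proportion of patients with at least a 5 point improvement in SF-36 individual domain scores" by logistic regression and Fisher's exact test with non-responder imputation, and labels it other secondary. SAP Section 4.3 lists the same responder endpoint as exploratory. Section 4.2 has only mean change in the domain scores as an other secondary endpoint.

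**The concern.** A point threshold has meaning only on the scale it was set for. The table puts the 5 points on 0-100, while the derivation it cites ends on another scale. A programmer who follows Appendix 1 as written would most naturally apply the cut to T-scores, where 5 points is half a normative SD and not 5 points of a 0-100 range. The same patient could then be a responder under the table and a non-responder under the appendix.

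At stake are eight responder proportions, one per domain. The choice of metric would be made in programming, without a record in the plan, and the reported percentages might not be those the table describes.

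**Working it through.** **Inputs from the SAP**

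- Cut: change of at least 5 points, beside a 0-100 range (Table RHBQ.6.4).
- T-score: mean 50, SD 10 (Appendix 1).
- PCS and MCS: norm 50, SD 10, with a cut of 2.5 points (Table RHBQ.6.4).
- Item counts and response ranges (Appendix 1): PF 10 items scored 1-3; RP 4, VT 4, RE 3, SF 2 and MH 5 items, all scored 1-5.
- Normative SD of each domain on 0-100: not printed. I assume 15 to 35 and show the range.

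The 5-point cut is a threshold, so there is no plan figure to reproduce.

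**Step 1: T-scores.** T = 50 + 10 × (x − mean)/SD. A change of d on 0-100 is therefore 10 × d/SD T-points, and 5 T-points equal 0.5 × SD points on 0-100. Relative to a cut of 5 on 0-100, the ratio is 0.5 × SD/5 = SD/10.

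| Assumed SD | 5 T-points on 0-100 | Ratio |
|---|---|---|
| 15 | 7.5 | 1.5 |
| 20 | 10.0 | 2.0 |
| 25 | 12.5 | 2.5 |
| 30 | 15.0 | 3.0 |
| 35 | 17.5 | 3.5 |

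The ratio is 1 at SD 10. The T-score cut is stricter for any larger SD.

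**Step 2: attainable scores.** One response category on one item moves the 0-100 score by 100/(items × category range): PF 100/20 = 5; MH 100/20 = 5; RP and VT 100/16 = 6.25; RE 100/12 = 8.33; SF 100/8 = 12.5. The smallest change that qualifies is the cut rounded up to a multiple of that step:

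| Domain | Cut 5 on 0-100 | T cut, SD 15 | SD 20 | SD 25 | SD 30 | SD 35 |
|---|---|---|---|---|---|---|
| PF, MH | 5 | 10 | 10 | 15 | 15 | 20 |
| RP, VT | 6.25 | 12.5 | 12.5 | 12.5 | 18.75 | 18.75 |
| RE | 8.33 | 8.33 | 16.67 | 16.67 | 16.67 | 25 |
| SF | 12.5 | 12.5 | 12.5 | 12.5 | 25 | 25 |

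The effect is uneven. SF does not change up to SD 25. GH and BP were not stepped, because their recalibrated items give uneven increments.

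**Step 3: raw sums.** These are also exported, but they are not 0-100 scores. Five raw points equal 5/20 = 25 points on 0-100 in PF and MH, 5/16 = 31.25 in RP and VT, 5/12 = 41.67 in RE, and 5/8 = 62.5 in SF. Exporting the raw sums therefore does not supply the stated metric.

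**Step 4: comparison within the SAP.** On the normed metric, 5 points is 5/10 = 0.5 SD. The PCS and MCS cut is 2.5/10 = 0.25 SD. The domain cut would be twice as strict, with no reason given.

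**The case against.** The best defence is that the range sentence is loose wording. Appendix 1, like protocol Section 8.1.2.2.6, gives the PCS and MCS a 0 to 100 range, although the SAP scores both on the 50/10 metric. No source is cited for the 5 points. If the cut was always meant for T-scores, only the range phrase is wrong and the analyses are as intended. This cannot be excluded. It is the weaker reading, because Table RHBQ.6.4 itself separates the two metrics: 50/10 with a cut of 2.5 for the summary scores, 0-100 with a cut of 5 for the domains.

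A second objection is that the export is ambiguous. Raw scores leave the software too, the columns name no metric, and Appendix 1 uses the term domain scores for the raw sums as well. That stands, and it makes T-scores the likelier reading but not the only one. It does not rescue the plan, since raw sums are not 0-100 scores either.

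Third, 5 points on 0-100 is a low bar: in six domains one category on one item reaches it. That is a fair criticism of the stated cut, but it does not tell the analyst which metric to use.

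**Conclusion.** The inconsistency is real. The cut is stated on 0-100, and neither score named for export is on that scale. If T-scores are used, the cut is SD/10 times the stated one, or 1.5 to 3.5 times for an assumed normative SD of 15 to 35.

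A reader might infer three stronger things that the documents do not support:

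- **That the cut is two to three times stricter throughout.** This needs normative SDs of 20 to 30, which the documents do not give. SF may not change at all.
- **That patients who improve by the stated amount will be counted as non-responders.** This depends on T-scores being the analysed metric, on the SD and on the domain.
- **That the trial's main conclusions are at risk.** The endpoint is outside the gatekept sequence, and SAP Section 4.3 calls it exploratory. Both arms share the same cut, so type I error and the primary and major secondary results are unaffected.

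What changes is who counts as a responder in up to eight analyses, and with it the response rates, their power and their interpretation. The point should be corrected, but it is not critical to the trial.

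**What to change.** Apply the 5-point rule to the 0-100 transformed domain score, as Table RHBQ.6.4 states, and add the eight 0-100 columns to the scoring export and the ADaM datasets. T-scores can stay for PCS and MCS, where the 2.5-point cut is already on the 50/10 metric.

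If the sponsor intended T-scores for the domain responders, correct the 0-100 range statement instead, and state a cut on the T-score metric with its source.

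Either way, name the metric in every domain row of Tables RHBQ.6.4 and RHBQ.6.5 and in the export table of Appendix 1. The endpoint's class should also be made the same in Section 4.3 and Table RHBQ.6.5.

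The cost is SAP wording plus at most eight variables that the derivation already computes. The downside of the 0-100 option is that a single response-category change on one item meets the cut in six domains (PF, MH, RP, VT, RE and SF), so responder rates would be higher in both arms than under a stricter T-score cut. The report should say so.
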